### **3.5 Study Statistics**

This study is planned as a descriptive study in an effort to quantify the psychological impact on ICU survivors of COVID-19. It is anticipated that the study will report its findings using descriptive methods in the absence of a comparator group.

Trajectories of anxiety, depression, and trauma symptoms will be estimated using growth curve analysis. To improve power, we will use the full range of anxiety, depression and trauma symptom scores (not cut-off scores). Growth modelling is latent variable covariance modelling to estimate the intercept (value of the initial observation) and slope (the rate of change from this observation over time) of a time series of mean scores. We will estimate full sample single class models (eg, assuming homogeneity across the sample) for each outcome. Initial fixed parameters will be; error variance constrained to equality across observations, mean intercept and slope constrained to zero, intercept and slope constrained to equality, and intercept and slope covariance constrained to zero. Parameters will be systematically relaxed in that order until good fitting models ( $CFI > .95$ ,  $RMSEA < .05$ ) are identified with maximum fixed parameters. Linear and quadratic slope models will be tested; linear models being defined as slope parameters 0, 1, 4, and 12 and quadratic slopes as 0, 1, 8 and 24.

We will estimate and predict individual survivors' slope and intercept scores. Scores will be calculated using the regression method, setting intercepts for observed variables to 0 and imposing equality of variance. We will then regress predictor variables onto intercept and slope scores for all outcomes to identify variables likely to determine trajectories of anxiety, depression and trauma symptoms.

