#### **Psychological assessment via self-reported questionnaire:**

The following four self-report questionnaires will be administered at 3, 6 and 12 months following ICU discharge:

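### Section 3.5 scores individual intercepts and slopes under an unnamed equality of variance that is not tied to the selected growth model, although equal error variance is the first constraint its search releases

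*Combined protocol and SAP*

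**What the plan says.** All the relevant text is in section 3.5 (Study Statistics) of the combined protocol and SAP.

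- Starting point of the search: "Initial fixed parameters will be; error variance constrained to equality across observations". The remaining starting constraints, in order, are "mean intercept and slope constrained to zero, intercept and slope constrained to equality, and intercept and slope covariance constrained to zero".
- Release rule: "Parameters will be systematically relaxed in that order until good fitting models" (CFI above .95, RMSEA below .05) "are identified with maximum fixed parameters".
- Scoring rule: "Scores will be calculated using the regression method, setting intercepts for observed variables to 0 and imposing equality of variance".
- Use of the scores: "We will then regress predictor variables onto intercept and slope scores for all outcomes".

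The plan does not say that the scores come from the selected model. It does not say which variance is made equal at scoring, or what happens if the search has already rejected that equality.

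**The concern.** Regression-method scores are weighted sums of a survivor's observed scores. The weights depend on the error variance at each wave and on the variances and covariance of intercept and slope. If the search frees the error variances because equality does not fit, and scoring then puts equality back, the weights belong to a model that the plan did not select.

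The scores are the only outcomes specified for the predictor analysis of anxiety, depression and trauma. What is at stake is the size of the reported predictor effects on slope. Two analysts following the sentence could also compute different scores: one might equate error variances and another the intercept and slope variances, and one might refit the model while another plugs in a common value.

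**Working it through.** The plan states no figure on this point, so there is none to reproduce. The check has two parts.

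**1. Is release of equal error variance likely?** The second starting constraint fixes the mean intercept and slope at zero. With observed-variable intercepts also at 0 (stated for scoring, assumed here for the search), such a model implies a mean of zero at every wave. HADS subscales run from 0 to 21 (section 3.3), so a sample with symptoms has a positive mean. With an assumed flat mean of 5 or 7, population RMSEA of the zero-mean model is about 0.44 to 0.55 under equal error variances, and it stays far above .05 when they are freed. Because constraints go in the listed order, error variances are freed before the means can be. On a cumulative reading, any model that passes has already released equality.

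**2. How much would re-imposed equality change the scores?**

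Input from the documents: questionnaires are "administered at 3, 6 and 12 months following ICU discharge". In three-month units from the first wave this gives loadings 0, (6−3)/3 = 1 and (12−3)/3 = 3.

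Assumed, not in the documents: intercept variance 12, slope variance 0.8, covariance −0.5 or 0, and the error variances in the table.

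Formula: with loading matrix L, intercept-slope covariance matrix Ψ and error matrix Θ, the score weights are W = ΨL′(LΨL′ + Θ)⁻¹. The expected response of the slope score to a unit of true slope is the (2,2) element of WL. This was computed three ways: *matched* (true Θ), *refitted* (equal-error model fitted by maximum likelihood) and *plugged in* (mean error variance, Ψ unchanged). RMSEA of the equal-error model is √(F/df), with F its minimum discrepancy. The df are 6 − 4 = 2 on the covariances alone, or 9 − 6 = 3 with the means.

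Results for covariance −0.5:

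| Error variance at 3/6/12 months | Matched | Refitted | Refitted ÷ matched | Plugged in ÷ matched | RMSEA (df 2 / df 3) |
|---|---|---|---|---|---|
| 6/6/6 | 0.41 | 0.41 | 1.000 | 1.000 | 0 / 0 |
| 7/6/5 | 0.43 | 0.37 | 0.853 | 0.955 | 0.050 / 0.041 |
| 8/6/5 | 0.42 | 0.36 | 0.850 | 0.946 | 0.080 / 0.065 |
| 9/6/4.5 | 0.43 | 0.33 | 0.769 | 0.914 | 0.117 / 0.095 |
| 10/6/4 | 0.44 | 0.30 | 0.685 | 0.879 | 0.152 / 0.124 |
| 5/6/7 | 0.40 | 0.45 | 1.137 | 1.036 | 0.052 / 0.042 |
| 5/6/8 | 0.37 | 0.48 | 1.279 | 1.065 | 0.068 / 0.055 |
| 4/6/9 | 0.37 | 0.51 | 1.395 | 1.085 | 0.121 / 0.099 |

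With covariance 0 the refitted ratios lie between 0.73 and 1.36 and the plugged-in ratios between 0.89 and 1.08.

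A second set of assumptions (intercept SD 4, SD of change 3, loadings 0,3,9 or 0,1,4 or 0,4,12) gives, for clearly unequal error variances (8,5,3 or 3,5,8), 0.64 to 1.41 refitted and 0.87 to 1.10 plugged in. A fourfold difference (10,5,2.5 or 2.5,5,10) gives 0.51 to 1.65 and 0.82 to 1.14.

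**Effect on detection.** In the tabulated scenarios with unequal variances (both covariances), slope scores from the matched and refitted models correlate at 0.94 to 0.997. For a predictor of slope alone, the signal-to-noise ratio (slope response divided by score SD) under refitted equality, relative to matched scores, is 0.88 to 1.01.

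**The case against.** The strongest case against has five parts.

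- *The variance is unnamed.* The scoring sentence does not say error variance, and the search also constrains intercept and slope to equality. If the latent variances are meant, the calculation above does not apply. This stands as a caveat. Error variance is still the likelier reading, because the phrase sits beside a constraint on the observed variables. The other reading does not rescue the sentence, since that equality can also be released in the search.
- *Release is conditional.* Constraints go only as far as fit requires, and the preference for maximum fixed parameters might let an analyst restore equality once the means are free. Mild inequality such as 7/6/5 gives an RMSEA of 0.041 to 0.053 over both covariances, which may pass. This stands: if equality is retained, there is no conflict.
- *The larger figures need a refit that the plan does not mention.* This stands; plugging in a common variance gives the smaller range.
- *Rescaling an outcome does not alter a predictor's test statistic.* This largely stands, as the signal-to-noise ratios show.
- *Shrinkage matters more.* Matched scores themselves carry only 0.37 to 0.45 of a true slope effect in the tabulated scenarios. This stands, and it is a separate issue.

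A reader might infer that the planned predictor effects are certainly mis-scaled, or that the predictor findings would be invalid. The documents support neither, because the variance is unnamed, release depends on the data and the method of imposing equality is not given. Nor are slope effects overstated in absolute terms when error rises over time: 0.48 to 0.51 exceeds the matched 0.37 to 0.39, but both lie well below 1.

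**Conclusion.** The point holds in a limited form. The scoring sentence is unconditional, while the constraint it most probably refers to is the first that the search gives up, and very likely will give up. The scores can then come from a model other than the selected one. That is an inconsistency in the plan and more than missing detail.

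Relative to matched scores, the scale of predictor effects on slope changes by nothing if error variances are equal, by about 4 to 13% if a common variance is plugged in, and by about 12 to 40% if the model is refitted with unequal variances. A fourfold difference in error variance would go further. Effects come out smaller when error falls over time and larger when it rises. All of this rests on assumed variances and three waves. Identification of predictors is little affected.

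The analysis concerned is exploratory in section 3.2 (secondary in the section 1 summary). The primary prevalence outcome does not use these scores.

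**What to change.** In the scoring sentence of section 3.5, delete the closing clause on equality of variance and add:

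> Scores will be calculated from the parameter estimates of the selected model for each outcome; variances are held equal only where that constraint was retained in the selected model.

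This settles the matter under either reading of the phrase and needs no new data.

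There is a small cost. Three waves give 3 means and 6 (co)variances, 9 moments in all. The linear model with free error variances uses 2 means, 2 variances, 1 covariance and 3 error variances, 8 parameters, which leaves 1 df. It is identified, but improper solutions are possible in smaller samples: about 4 to 10% of simulated samples at n = 300 and under 0.5% at n = 1000, with covariance −0.5. Section 3.6 does not guarantee 1000 complete responders, so a line on handling improper solutions would help.

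The change does not remove the shrinkage; entering predictors directly into the growth model would be a separate decision. Section 3.5 also gives four loadings ("linear models being defined as slope parameters 0, 1, 4, and 12") for three questionnaire times, which must be reconciled before any score can be computed.

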Main Inclusion and Exclusion Criteria	
Inclusion criteria:
 
 
1. Adult patients <math>\geq 18</math> years
 
2. Survived to intensive care / high dependency unit discharge following an admission of <math>\geq 24</math> hours
 
3. Diagnosed positive for COVID-19
 
 
Exclusion criteria:
 
 
1. Unable to complete questionnaires
 
2. Unable or unwilling to consent
 
3. Unable to speak, understand or communicate in English
 
4. Patients with diagnosed pre-existing cognitive impairment (at the time of ICU admission)
 
5. Patients with no fixed abode, at which postal questionnaire might be not received, and who have no access to a personal email address.
 

Randomisation	Not applicable
Statistical Methodology and Analysis	Trajectories of anxiety, depression, and trauma symptoms will be estimated using growth curve analysis. We will estimate and predict individual survivors' slope and intercept scores. We will then regress predictor variables onto intercept and slope scores for all outcomes to identify variables likely to determine trajectories of anxiety, depression and trauma symptoms. Feasibility will be assessed using descriptive analyses.

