##### **Exploratory objectives:**

1. Identify demographic, clinical, physical and/or psychosocial predictors of depression, anxiety and/or trauma symptoms at 3-, 6- and 12-months after ICU discharge in patients being treated for COVID-19 within the ICU.
2. Assess the feasibility of using a self-reported questionnaire to assess anxiety, depression and/or trauma symptoms in patients following ICU admission with COVID-19.
3. Explore the experiences of critical care survivors following COVID-19 infection during their recovery phase, including perceptions about the care received and support available to them, using semi-structured interviews.
4. Assess geographical differences in the availability and structure of follow-up services offered to patients with critical COVID-19 after hospital discharge.
5. Gain feedback from the study team members on their involvement in this trainee-led study.

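### Relating predictors to saved regression-method intercept and slope scores gives shrunken, mixed effects; put the predictors inside the growth model

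*Combined protocol and SAP*

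**What the plan says.** Section 3.5 describes growth modelling as a way to "estimate the intercept (value of the initial observation) and slope (the rate of change from this observation over time", so the intercept is the level at the first questionnaire. The models are fitted to the whole sample as a single class, without predictors. Individual values are then saved: "Scores will be calculated using the regression method, setting intercepts for observed variables to 0 and imposing equality of variance". The second step is "We will then regress predictor variables onto intercept and slope scores for all outcomes to identify variables likely to determine trajectories". The Study Summary repeats it: "We will then regress predictor variables onto intercept and slope scores for all outcomes".

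Two other features of section 3.5 matter here. The model search begins with "intercept and slope covariance constrained to zero", the last constraint on its list, and "Parameters will be systematically relaxed in that order until good fitting models" are found. The time coding is given as "linear models being defined as slope parameters 0, 1, 4, and 12", which is four values, although section 5.3 schedules three questionnaires (3, 6 and 12 months).

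The objective served is in section 3.2: "Identify demographic, clinical, physical and/or psychosocial predictors of depression, anxiety and/or trauma symptoms at 3-, 6- and 12-months after ICU discharge". It is labelled exploratory there and secondary in the Study Summary. Nothing in the document places predictors inside the growth model, uses unshrunk scores, corrects the second-step coefficients or carries the uncertainty of the scores forward.

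**The concern.** A regression-method score is a shrunken prediction. With three noisy measurements per person, the slope score leans heavily on the group mean and borrows from the person's level. Used as the outcome of a second regression, it passes that shrinkage and borrowing on to every predictor coefficient.

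The analysis is meant to separate variables that go with a worse start from variables that go with a different course. Under the planned method, a variable that only raises the 3-month level can be reported as a predictor of change. A variable that goes with a worse start but faster recovery can be missed. The bias in the slope coefficient can go either way, so a reader cannot allow for it afterwards.

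The wording also leaves the direction open. Read literally, the predictor is regressed on the scores. With both scores entered together, most of the bias would then disappear, but the result would not show what determines a trajectory.

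**Working it through.** **Plan's own figure.** The only related arithmetic is in section 3.6: 1000 / 0.40 = 2500 questionnaires. It reproduces and is not in dispute. The plan gives no variances; section 3.3 lists the HADS standard deviation among quantities still to be estimated. All sizes below are therefore assumptions.

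**Formula.** Let L have rows (1,0), (1,3), (1,9), in months after the first questionnaire. Let Ψ be the covariance matrix of intercept and slope, θ the residual variance, and Γ the true effects of a predictor on intercept and slope. The scores are ΨL'(LΨL' + θI)⁻¹ times the centred data. Their regression on the predictor therefore has expectation A·Γ, with A = ΨL'(LΨL' + θI)⁻¹L. A equals the identity only without measurement error.

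**Worked case.** Intercept variance 12.5, slope variance 0.08, correlation -0.2, θ = 5. The covariance is -0.2 × √(12.5 × 0.08) = -0.2, and

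A = [0.858, 1.910; 0.0052, 0.420].

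- Slope-only effect of 0.05 points/month: the slope coefficient is 0.420 × 0.05 = 0.021, and 1.910 × 0.05 = 0.096 appears on the intercept.
- Level +1.0 and slope -0.05: the slope coefficient is 0.0052 - 0.0210 = -0.016 instead of -0.05.

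**Grid of 216 settings.** Intercept variance 8/12.5/16; slope variance 0.02/0.03/0.05/0.08/0.15/0.30; correlation -0.5/-0.2/0/+0.2; θ 2/5/8.

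| True effect (level; slope per month) | Expected slope result |
|---|---|
| 0; +0.05 | share kept 0.04 to 0.89, median 0.40 |
| +1.0; +0.05 | -0.010 to +0.077; at or above the truth in 39 settings, negative in 18 |
| +1.0; -0.05 | -0.042 to +0.011; wrong sign in 32 |

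**Simulation.** Intercept variance 12.5, θ = 5, standard-normal predictor, growth model re-estimated in every run, two-sided 5% test, N = 1000 unless stated. Lists of four are for slope variance 0.03/0.08/0.15/0.30. With complete data, the one-step comparator equals regression on unshrunk (Bartlett) scores.

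| Level-only predictor, 1.0 point: declared a slope predictor | Two-step | One-step |
|---|---|---|
| correlation -0.2 | 26/20/22/21% | 4-6% |
| correlation 0 | 68/60/49/33% | 4-6% |
| correlation +0.2 | 95/87/72/47% | 4-6% |

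A repeat with 600 runs per setting gave 26/18/22/21%, 65/60/44/29% and 93/86/73/45%. At correlation -0.5 it gave 94/41/9/8%. At correlation -0.2 and slope variance 0.03 the expected leak is practically zero (-0.0001), yet 26% of runs reject. With A taken as known the rate there is 5%. The excess arises because A is estimated while the second-step standard error treats it as fixed.

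- Level-only, 0.5 points: 11/10/10/9% (correlation -0.2), 30/21/17/12% (0), 62/37/25/17% (+0.2).
- Level-only, 1.0 point, N = 200: 10-30% (-0.2) and 15-47% (+0.2).
- Slope-only, true 0.05, correlation -0.2: the estimate is 0.010/0.021/0.030/0.038. Coverage of the 95% interval is 0/1/38/87%, and 4/35/77/92% at N = 200. One-step: 0.048-0.051, coverage 94-96%.
- Level +1.0 and slope -0.05: faster recovery detected in 93/76/53/30% (-0.2), 42/31/22/15% (0) and 7/7/8/8% (+0.2), against 98/94/86/67-69% one-step.

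**Conditional on the model search.** If the search stops while the covariance is still wrongly fixed at zero, and scores come from that model (the plan does not say), the error rate changes again. At correlation -0.2 that model meets both fit limits in about 72/46/25/10% of samples. It does so and also gives a false slope finding for a 1.0-point level predictor in 58/31/14/6%. At correlation -0.5 it passed in none of 200 samples per setting; at +0.2 a zero covariance lowers the false-finding rate.

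**Literal direction.** With the predictor as response and both scores entered (level 1.0, slope 0.05, worked-case variances), the true coefficients are 0.094 and 0.859, and the estimates 0.094 and 0.873.

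**The case against.** The mechanism is not in dispute once the scores are the outcome. The objections concern weight.

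1. *The objective is modest.* It is exploratory in section 3.2, asks about symptoms at set times, and does not touch the primary estimate. This limits the severity. But levels at set times are biased too: in the worked case a true level effect of 1.0 becomes 0.858 at 3 months and 0.858 + 9 × 0.0052 = 0.905 at 12 months.
2. *The plan states no test.* The 5% rule is an assumption of this check. The biased coefficients and poor interval coverage do not depend on it.
3. *The leak is small in points.* For a 1.0-point level effect and the simulation variances, it is at most about 0.016 points/month at correlation -0.2 and 0.028 at +0.2, or 0.15 and 0.25 points over nine months on a 0-21 scale. That is correct. A slope effect of 0.05/month is itself only 0.45 points over that time, so the leak is not negligible beside it.
4. *Grid counts are not probabilities.* Correct. Of the 32 wrong-sign settings, 26 are at correlation +0.2, 6 at 0 and none at a negative correlation. All 18 negative settings in the second row are at -0.5.
5. *Some settings are benign.* Correct. For a 0.5-point effect with N = 200 and slope variance of at least 0.08, rates are about 6-12%. Section 3.6 makes N = 1000 a target only.
6. *The plan's own loadings are kinder.* With 0, 1, 4, 12 the median share kept is 0.58 and the wrong-sign settings fall to 2. The bias remains, and those loadings do not fit three visits.
7. *Power for slope-only predictors is not lost.* Correct: at correlation -0.2, 98/96/89/72% against 98/95/87/69% one-step. The harm is misattribution, biased coefficients and wrong intervals.

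**Conclusion.** The concern holds. With the scores as the outcome, shrinkage and mixing follow from the algebra of the scoring method; only their size depends on quantities the plan does not give. Under the assumptions shown, slope effects keep 4% to 89% of their value. Level-only predictors can be declared predictors of change far more often than 5%, and intervals for slope-only effects can cover almost never. The size and sometimes the sign of the error depend on the unknown intercept-slope correlation. Predictors unrelated to both level and change are not affected (4-6% rejection), nor is the primary prevalence estimate. The simulations assume complete data at three waves and HADS-like variances. The point is worth correcting before analysis but does not threaten the main result.

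**What to change.** In section 3.5 and the Study Summary, state that the latent intercept and slope are the outcomes. Replace the two steps with one conditional latent growth model per outcome:

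- predictors entered as covariates of the latent intercept and slope;
- intercept-slope covariance estimated freely;
- all available waves used;
- slope loadings matched to the three questionnaires, for example 0, 3 and 9 months after the first, with the quadratic coding revised likewise (it also lists four values);
- for EQ-5D-5L and CAS-1R, which are measured at every wave, the first-questionnaire (3-month) value;
- coefficients with 95% confidence intervals reported from this model, and individual scores used for description only.

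The cost is wording in two places; the data and the type of software stay the same. A rule for missing predictor values becomes necessary, including for people who skip the 3-month questionnaire and answer later ones, as section 5.2 allows. Because the 3-month EQ-5D-5L and CAS-1R are collected together with the 3-month outcomes, their link to the intercept is cross-sectional. Only their link to the slope is prospective, and the report should say so.

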#### **3.2 Study Objectives**

##### **Primary objective:**

To identify the proportion of patients who survive ICU admission following treatment for COVID-19 that experience anxiety, depression and/or trauma symptoms at 6 months, assessed using the Hospital Anxiety and Depression Scale (HADS) and the Impact of Event Scale-6 (IES-6), respectively.

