**Exploratory outcomes:**

1. Identify demographic, clinical, physical and/or psychosocial predictors of depression, anxiety and/or trauma symptoms at 3-, 6- and 12-months post discharge from ICU.

a. Demographic and clinical predictors.

(See Schedule of Study Procedure for specific data that will be collected.)

b. Physical predictors.

The EuroQol 5-dimension, 5-level questionnaire (EQ-5D-5L) is a five-domain, self-report measure assessing mobility, self-care, usual activities, pain/discomfort and anxiety/depression. Participants are asked to rate each question, indicating no problems, slight problems, moderate problems, severe problems or extreme problems. In addition, participants are invited to rate their health on a visual analogue scale from 0-100, where zero represent the worst health imaginable and 100 represents the best health imaginable. EQ-5D-5L is the recommended questionnaire to assess the HRQoL of critically ill patients (26). In this study, EQ-5D-5L will be used as a subjective assessment of the physical function of participants.

c. Psychosocial predictors (metacognitive beliefs and processes).

Metacognitive beliefs and processes will be assessed using the Cognitive Attentional Syndrome Scale-1 (Revised; CAS-1R (27)). The CAS-1R is a 10-item self-report measure assessing positive and negative metacognitive beliefs, frequency of worry/rumination and the use of a range of counterproductive coping strategies used in response to negative thoughts and feelings. Participants are asked to rate the degree to which they have engaged in a particular coping strategy or thought process during the previous week. Responses are scaled from 0%-100% and are summed to produce a total score. Higher scores indicate greater conviction in metacognitive beliefs and greater use of maladaptive coping strategies to manage distress. The CAS-1R has demonstrated good psychometric properties in physical health populations.

2. Assess the feasibility of using a self-reported online questionnaire to assess anxiety, depression and/or trauma symptoms in patients following ICU admission.

Outcomes:

- Recruitment number (total number of patients recruited per month)
- Recruitment rate (proportion of those deemed eligible recruited)
- Retention rate (proportion of participants who provide data at subsequent data capture points)
- Rate of missing key data
- Estimation of quantities needed for an accurate sample size calculation (e.g. HADS standard deviation)

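### Exploratory objective 1 asks for predictors of symptoms at 3, 6 and 12 months, but section 3.5 specifies predictor effects only on the intercept (3 months) and the slope, and the 6- and 12-month effects cannot be reliably recovered from these

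*Combined protocol and SAP*

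**What the plan says.** Section 3.2 lists as its first exploratory objective the identification of "predictors of depression, anxiety and/or trauma symptoms at 3-, 6- and 12-months after ICU discharge in patients being treated for COVID-19". Section 3.3 repeats it among the exploratory outcomes: "psychosocial predictors of depression, anxiety and/or trauma symptoms at 3-, 6- and 12-months post discharge from ICU". The Study Summary has the same objective but calls it secondary.

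Section 3.5 contains one predictor analysis. Growth modelling is to "estimate the intercept (value of the initial observation) and slope (the rate of change from this observation over time". Each patient's intercept and slope scores are then predicted by the regression method, and the plan states: "We will then regress predictor variables onto intercept and slope scores for all outcomes to identify variables likely to determine trajectories". The Study Summary repeats this: "We will then regress predictor variables onto intercept and slope scores for all outcomes".

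The questionnaires are given at 3, 6 and 12 months after ICU discharge (section 5.3), so the initial observation is the 3-month one. Section 3.5 defines the linear slope by four loadings, 0, 1, 4 and 12, and the quadratic slope by 0, 1, 8 and 24. Nothing plans a regression at 6 or 12 months, moves the intercept to those visits, or says that the two sets of coefficients will be combined into an effect at a visit.

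**The concern.** Level at a visit and rate of change are different targets. The objective is written for the first at three named times. The analysis delivers the first at 3 months only, plus the second.

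The two can tell different stories. Suppose, for illustration, that a predictor is worth +1.5 HADS points at 3 months and its slope effect is -0.17 points per month. Its effect at 6 months is 1.5 - 0.17 x 3 = 0.99, and at 12 months 1.5 - 0.17 x 9 = -0.03. The plan would list this variable as associated with both scores and would never show that it makes almost no difference at 12 months. Conversely, a variable with no intercept effect and a modest slope effect could matter clearly at 12 months.

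At stake is whether the study answers its predictor objective at 6 and 12 months from a pre-specified analysis, or whether that answer is assembled after the results are seen.

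**Working it through.** **The plan's own figures.** The plan states no figure for this analysis. The only sample-size arithmetic (section 3.6: 2500 sent x 0.40 returned = 1000) reproduces, but has no bearing here.

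**Step 1: what a linear growth model implies.** With loading k(t) for visit t, the predictor effect at that visit is

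b(t) = b_intercept + k(t) x b_slope.

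So effects at 6 and 12 months exist in principle. The question is whether the planned output yields them.

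**Step 2: which loading belongs to which visit.** There are three visits and four loadings. Three-month units from the first visit would give 0, 1, 3, which is not a subset of 0, 1, 4, 12. Take assumed effects b_intercept = 1.0 and b_slope = -0.2 per unit:

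| Loadings used for 3, 6, 12 months | 3 months | 6 months | 12 months |
|---|---|---|---|
| 0, 1, 3 (actual spacing) | 1.0 | 0.8 | 0.4 |
| 0, 1, 4 | 1.0 | 0.8 | 0.2 |
| 0, 4, 12 | 1.0 | 0.2 | -1.4 |
| 0, 1, 12 | 1.0 | 0.8 | -1.4 |
| 1, 4, 12 | 0.8 | 0.2 | -1.4 |

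The same two coefficients imply a 12-month effect anywhere from 0.4 to -1.4.

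**Step 3: what the score regressions estimate, even with correct loadings.** Assumptions, none of them from the documents: loadings 0, 1, 3; intercept variance 12, slope variance 0.6, no covariance, error variance 6; a predictor with variance 1; true effects b = (1, -1/3), so the effects at the three visits are 1.00, 0.67 and 0.00. Let L be the 3 x 2 loading matrix, G = diag(12, 0.6) + b b', and S = L G L' + 6 I. The regression-method score is G L' S^-1 (y - mean), so regressing scores on the predictor gives in expectation

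A b, with A = G L' S^-1 L = [0.834, 0.688; 0.026, 0.383].

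If the scores carried the effects through unchanged, A would be the identity matrix. Instead:

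- intercept score: 0.834 x 1 + 0.688 x (-0.333) = about 0.60;
- slope score: 0.026 x 1 + 0.383 x (-0.333) = about -0.10.

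Combining them gives 0.60 at 3 months, 0.60 - 0.10 = 0.50 at 6 months and 0.60 - 3 x 0.10 = 0.30 at 12 months, against true effects of 1.00, 0.67 and 0.00. In a simulation of 400,000 patients under the same assumptions, a regression at each visit returned 1.01, 0.66 and 0.00.

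**Step 4: how far this depends on the assumptions.** Repeating step 3 and changing one variance at a time, the combined 12-month effect (truth 0.00) is 0.19 with error variance 2, 0.32 with error variance 10, 0.19 with slope variance 2 and 0.37 with slope variance 0.2. The error can also go the other way. With true effects (0, 1/3), the 12-month value is 0.62 against a truth of 1.00. With (1, 0), it is 0.93 against 1.00.

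**The case against.** The strongest reply is that the gap is narrow. A growth model implies an effect at every visit, section 3.5 says openly that its aim is to explain trajectories, and sections 2 and 3.1 state the predictor aim without time points. The list of months in the objective may only describe the questionnaire schedule. This has some force: rewording the objective to predictors of trajectory would also remove the mismatch. But the months appear in the objective in three places, and as written they define when predictors are wanted.

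Four stronger readings are tempting, and the documents do not support them:

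- **That no predictor effect at 6 or 12 months is estimated at all.** The linear model implies one. It is unspecified, unreported and poorly recoverable, not absent.
- **That the study loses predictors at its primary time point.** Six months is primary for the prevalence objective, the proportion who "experience anxiety, depression and/or trauma symptoms at 6 months". The predictor objective is exploratory and does not rank its three visits.
- **That two separate regressions lack the covariance needed for an interval.** One could regress the combined score (intercept plus k times slope) directly and obtain an interval. That interval would still be centred on the shrunken value in step 3.
- **That the 6-month effect would be twice as precise as the intercept effect.** For a line through times 0, 3 and 9 months, the residual-error factors 1/3 + (t - 4)^2/42 are 0.714, 0.357 and 0.929, but between-patient variance must be added. With the assumed variances the totals are 12 + 0.714 x 6 = 16.3 at 3 months and 12.6 + 0.357 x 6 = 14.7 at 6 months, about 10% lower rather than half.

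**Conclusion.** The mismatch stands. Followed as written, section 3.5 reports predictor effects on the 3-month level and on the slope, and none at 6 or 12 months. Deriving them afterwards is unsafe because the loadings do not map to the three visits and the score coefficients are shrunken and mixed.

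The mismatch and the loading problem rest on the text alone. The size of the distortion rests on assumed variances and effects. In the cases tried, a true 12-month effect of zero appeared as 0.19 to 0.37 when the 3-month effect was 1.00, and a true 12-month effect of 1.00 appeared as 0.62 to 0.93.

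Because the objective is exploratory, this does not touch the primary result. It is worth correcting before analysis, since it decides whether the study can answer its own predictor question.

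**What to change.** Add to section 3.5: *For each outcome, predictors will be entered directly in the growth model in one step, with slope loadings that match 3, 6 and 12 months and with the intercept-slope covariance freely estimated. Each predictor's effect on the symptom score, with 95% CI, will be reported at 3, 6 and 12 months, by re-centring or as a model contrast. Slope effects will be reported in addition.*

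Three details matter:

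- **One step.** Saved scores bring back the shrinkage, so predictors must enter the model itself.
- **Free covariance.** Section 3.5 starts with the intercept-slope covariance at zero and keeps as many constraints as fit allows. Zero covariance at the first visit becomes k x Var(slope) at a visit with loading k, so re-centring under that constraint would fit a different model.
- **No ranking.** The three visits need no order of importance for an exploratory objective.

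A regression at each visit would also serve. It does not assume a straight line, but uses only patients who answered at that visit. If the investigators want trajectories only, they should reword the objective in the Study Summary and sections 3.2 and 3.3. The loadings would still need correcting.

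The cost is a short addition to section 3.5, a few extra runs per outcome and no new data. Per predictor, 3 outcomes x (3 visits + 1 slope) = 12 estimates replace 3 x 2 = 6.
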